Appendix F – Protocol Deviation Log

Site _____

Protocol deviations must be reported to [name] (FANO) within 48 hours of discovery. [name] is responsible for keeping the Protocol Deviation Log.

Protocol Deviation Code:	Participant Initials	Participant ID#	Date Deviation Occurred: mm/dd/yyyy	Date Protocol Deviation Documented: mm/dd/yyyy	Contact Person (if applicable)	Notes
PROTOCOL DEVIATION CODES						

Consent Form:
 
 1. Missing or not obtained 2. Not signed and dated by participant 3. Does not contain all required signatures 4. Outdated; current IRB-approved version not used 
Randomization:
 
 5. Ineligible participant enrolled and/or randomized 6. Participant is randomized prior to determining whether eligible for study. 7. Participant randomized prior to completing baseline survey 
IRB:
 
 8. Not reporting a serious complication within 24 hours; 9. Approvals not kept up to date 10. Enrollment and/or treatment occurs prior to IRB approval or during period when on “on hold.” 11. Reportable serious adverse events not reported to IRB 			
Participant
 
 12. Receives wrong intervention (immediate vs waitlist) 13. Visits occur outside expected follow-up window 14. Entered into another diabetes study 
Study Data and/or Forms
 
 15. Missing HbA1c 16. Missing surveys 17. Forms or data not sent from clinical site to coordinating center 			

Appendix G – MOP Modification Log

MOP Modification Log

Protocol Name: Feeding America Intervention Trial for Health – Diabetes Mellitus

MOP MODIFICATION LOG					
VERSION #	SECTION #	PAGE #	DATE MODIFIED	A / D / R **	BRIEF MODIFICATION SUMMARY

** **A** = Addition, **D** = Deletion, **R** = Revision

This log is the responsibility of the Coordinating Center.

Appendix H – CONSORT 2010 Checklist**CONSORT 2010 checklist of information to include when reporting a randomised trial***

Section/Topic	Item No	Checklist item	Reported on page No
Title and abstract			
	1a	Identification as a randomised trial in the title	_____
	1b	Structured summary of trial design, methods, results, and conclusions (for specific guidance see CONSORT for abstracts)	_____
Introduction			
Background and objectives	2a	Scientific background and explanation of rationale	_____
	2b	Specific objectives or hypotheses	_____
Methods			
Trial design	3a	Description of trial design (such as parallel, factorial) including allocation ratio	_____
	3b	Important changes to methods after trial commencement (such as eligibility criteria), with reasons	_____
Participants	4a	Eligibility criteria for participants	_____
	4b	Settings and locations where the data were collected	_____
Interventions	5	The interventions for each group with sufficient details to allow replication, including how and when they were actually administered	_____
Outcomes	6a	Completely defined pre-specified primary and secondary outcome measures, including how and when they were assessed	_____
	6b	Any changes to trial outcomes after the trial commenced, with reasons	_____
Sample size	7a	How sample size was determined	_____
	7b	When applicable, explanation of any interim analyses and stopping guidelines	_____
Randomisation:			
Sequence	8a	Method used to generate the random allocation sequence	_____
generation	8b	Type of randomisation; details of any restriction (such as blocking and block size)	_____

Allocation concealment mechanism	9	Mechanism used to implement the random allocation sequence (such as sequentially numbered containers), describing any steps taken to conceal the sequence until interventions were assigned	<hr/>
Implementation	10	Who generated the random allocation sequence, who enrolled participants, and who assigned participants to interventions	<hr/>
Blinding	11a	If done, who was blinded after assignment to interventions (for example, participants, care providers, those assessing outcomes) and how	<hr/>
	11b	If relevant, description of the similarity of interventions	<hr/>
Statistical methods	12a	Statistical methods used to compare groups for primary and secondary outcomes	<hr/>
	12b	Methods for additional analyses, such as subgroup analyses and adjusted analyses	<hr/>
Results			
Participant flow (a diagram is strongly recommended)	13a	For each group, the numbers of participants who were randomly assigned, received intended treatment, and were analysed for the primary outcome	<hr/>
	13b	For each group, losses and exclusions after randomisation, together with reasons	<hr/>
Recruitment	14a	Dates defining the periods of recruitment and follow-up	<hr/>
	14b	Why the trial ended or was stopped	<hr/>
Baseline data	15	A table showing baseline demographic and clinical characteristics for each group	<hr/>
Numbers analysed	16	For each group, number of participants (denominator) included in each analysis and whether the analysis was by original assigned groups	<hr/>
Outcomes and estimation	17a	For each primary and secondary outcome, results for each group, and the estimated effect size and its precision (such as 95% confidence interval)	<hr/>
	17b	For binary outcomes, presentation of both absolute and relative effect sizes is recommended	<hr/>
Ancillary analyses	18	Results of any other analyses performed, including subgroup analyses and adjusted analyses, distinguishing pre-specified from exploratory	<hr/>
Harms	19	All important harms or unintended effects in each group (for specific guidance see CONSORT for harms)	<hr/>
Discussion			
Limitations	20	Trial limitations, addressing sources of potential bias, imprecision, and, if relevant, multiplicity of analyses	<hr/>
Generalisability	21	Generalisability (external validity, applicability) of the trial findings	<hr/>

Interpretation	22	Interpretation consistent with results, balancing benefits and harms, and considering other relevant evidence	_____
----------------	----	---	-------

Other information

Registration	23	Registration number and name of trial registry	_____
--------------	----	--	-------

Protocol	24	Where the full trial protocol can be accessed, if available	_____
----------	----	---	-------

Funding	25	Sources of funding and other support (such as supply of drugs), role of funders	_____
---------	----	---	-------

*We strongly recommend reading this statement in conjunction with the CONSORT 2010 Explanation and Elaboration for important clarifications on all the items. If relevant, we also recommend reading CONSORT extensions for cluster randomised trials, non-inferiority and equivalence trials, non-pharmacological treatments, herbal interventions, and pragmatic trials. Additional extensions are forthcoming: for those and for up to date references relevant to this checklist, see www.consort-statement.org.

Appendix I – Passive Diabetes Self-Management Education Materials

AADE7 Self-Care Behaviors

1. Healthy Eating
2. Being Active
3. Monitoring
4. Taking Medication
5. Problem Solving
6. Reducing Risks
7. Healthy Coping

Study participants will receive 11 sets of passive education materials over a six-month period. Each set will be included with one of the bi-monthly food box distributions. This schedule was designed so that all participants, regardless of what week during the year they enroll and enter the study, will receive nearly identical sets of education materials over the course of their participation.

Time Frame	Subject Area	Resources	Recipes	Notes
Enrollment	Introduction to FAITH-DM; Basic Diabetes Information	FAITH-DM Welcome Letter and Resources; ACP Guide (intervention arm only); LAD – What’s My A1C?	** Project staff at food bank sites will develop diabetes-appropriate recipes based on current food inventory, participant preferences, etc.	Participant also receives weekly materials with 1 st box at time of enrollment; participants in control group receive ACP guide and first set of weekly materials with first food package pick-up after 6-month waiting period
January – week 1	Healthy Eating 1	LZ – Diabetes MyPlate, Portion Distortion		
January – week 2	Being Active 1	IDC – Activity Pyramid LAD – My Weekly Exercise Plan		
February – week 1	Healthy Coping 1	IDC – Life Balance Pyramid; LAD – Diabetes and Depression		
February – week 2	Problem Solving	LAD – Saving Money on Medicines, Diabetes Supplies, Sick Days with Diabetes		
March – week 1	Reducing Risks 1	LAD – Tips for Good Foot Care, Diabetes and Your Eyes; State-		

Time Frame	Subject Area	Resources	Recipes	Notes
		specific smoking cessation info		
March – week 2	Monitoring	LAD – Blood Sugar Meters, Blood Sugar Diary, Low Blood Sugar, High Blood Sugar		
April – week 1	Taking Medication	LAD – Your Diabetes Pills, Diabetes Pills - Actions, Medicines You Inject - Actions		
April – week 2	Healthy Eating 2	LZ – MyPlate on a Budget, Sugar Shockers		
May – week 1	Being Active 2	LAD – Let’s Get Moving, Walking Works		
May – week 2	Reducing Risks 2	LAD – High Blood Pressure and Diabetes, Cholesterol and Diabetes, Diabetes Care Schedule		
June – week 1	Healthy Eating 3	LAD – The Nutrition Facts Label; Healthy Cooking Tips		
June – week 2	Healthy Coping 2	LAD – Diabetes and Stress; My Goal This Month		
July – week 1	Healthy Eating 1	LZ – Diabetes MyPlate, Portion Distortion		
July – week 2	Being Active 1	IDC – Activity Pyramid LAD – My Weekly Exercise Plan		
August – week 1	Healthy Coping 1	IDC – Life Balance Pyramid; LAD – Diabetes and Depression		
August – week 2	Problem Solving	LAD – Saving Money on Medicines, Diabetes Supplies, Sick Days with Diabetes		
September – week 1	Reducing Risks 1	LAD – Tips for Good Foot Care, Diabetes		(Begin participant enrollment, 2015)

Time Frame	Subject Area	Resources	Recipes	Notes
		and Your Eyes; State-specific smoking cessation info		
September – week 2	Monitoring	LAD – Blood Sugar Meters, Blood Sugar Diary, Low Blood Sugar, High Blood Sugar,		
October – week 1	Taking Medication	LAD – Your Diabetes Pills, Diabetes Pills - Actions, Medicines You Inject – Actions		
October – week 2	Healthy Eating 2	LZ – MyPlate on a Budget, Sugar Shockers		
November – week 1	Being Active 2	LAD – Let’s Get Moving, Walking Works		
November – week 2	Reducing Risks 2	LAD – High Blood Pressure and Diabetes, Cholesterol and Diabetes		
December – week 1	Healthy Eating 3	LAD – The Nutrition Facts Label; Healthy Cooking Tips		
December – week 2	Healthy Coping 2	LAD – Diabetes and Stress; My Goal This Month		

LZ = [Learning Zone Express](#)

- Diabetes MyPlate
- Portion Distortion
- MyPlate on a Budget
- Sugar Shockers
- USDA MyPlate (screening resource only for clients with A1C result < 5.7%)

LAD = [Learning About Diabetes](#)

- What's My A1C
- My Weekly Exercise Plan
- Diabetes and Depression
- Saving Money on Medicines
- Diabetes Supplies
- Sick Days with Diabetes
- Tips for Good Foot Care
- Diabetes and Your Eyes
- Blood Sugar Meters
- Blood Sugar Diary
- Low Blood Sugar
- High Blood Sugar
- Your Diabetes Pills
- Diabetes Pills – Actions
- Medicines You Inject – Actions
- Let's Get Moving
- Walking Works
- High Blood Pressure and Diabetes
- Cholesterol and Diabetes
- Diabetes Care Schedule
- The Nutrition Facts Label
- Healthy Cooking Tips
- Diabetes and Stress
- My Goal This Month

ACP = [American College of Physicians](#)

- Diabetes Guides

IDC = [International Diabetes Center](#)

- The Activity Pyramid
- The Life Balance Pyramid

State Smoking Cessation Resources

- CA: <http://www.nobutts.org/>
- MI: http://www.michigan.gov/healthmichigan/0,4675,7-216-33084_33091_33302---,00.html
- TX: <http://www.yesquit.org>

Appendix J – Screening Results Form [English]

Thank you for having your blood sugar and/or hemoglobin A1c (A1C) checked here today. Your A1C tells you what your average blood sugar was for the last three months. If your A1C is high, you may have diabetes. For people who already have diabetes, a common goal is to have an A1C close to 7%.

Your blood sugar is: _____ mg/dL (normal is 70 – 160)

Your A1C is: _____ %

- This is normal (A1C 5.6% or less).
- This is a little high (A1C 5.7% - 6.4%). You may have pre-diabetes. We suggest you see your doctor to find out for sure whether you have pre-diabetes.
- This is high (A1C 6.5% or higher). You may have diabetes. We suggest you see your doctor to find out for sure whether you have diabetes.

Your A1C test result is not a diagnosis of pre-diabetes or diabetes. Only a doctor can tell you whether you have pre-diabetes or diabetes, or if your diabetes is well-controlled. Please see the back of this form for information about community health care centers and additional food resources.

(Site Specific Information)

Food Resources

- Food Bank:
- SNAP:
- Special Nutrition Program for Women, Infants, and Children (WIC):

Community Health Centers & Programs

- Clinic 1
- Clinic 2
- Clinic 3
- Clinic 4
- Local DPP
- Local DSME Program

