3.1.1 Testing for diabetes and diabetes control among food pantry clients

In order to identify food bank clients who may be eligible for study participation, food bank project staff will offer free diabetes screening events at food pantry sites during the recruitment phase of the study. Diabetes screening will be provided at no cost for any food pantry client who is interested in and verbally consents to the screening, and is over 18 years of age. Food bank staff will conduct all screening activities, emphasizing with food pantry clients that screening tests are **not** diagnostic and that clients should speak directly with their health care providers for diabetes risk assessment, evaluation, and treatment.

For food pantry clients with no reported history of diabetes, or no known history of diabetes, diabetes screening will first include a random blood glucose (RBG) test using a Point-of-Care (POC) glucometer and a finger stick capillary whole blood sample. Clients who have an elevated RBG screening result (defined as ≥ 160 mg/dL in non-fasting individuals and ≥ 140 mg/dL in fasting individuals) will also receive a screening glycosylated hemoglobin A1C (HbA1c) test using a POC device.

All screening tests will be performed by trained study or food bank staff, or by trained food bank volunteers. All study staff and volunteers with human subjects contact must have appropriate CITI certification and quality and safety training. Screening staff will complete the information on the Screening Log (Appendix B) for **every** food pantry client who receives a blood glucose and/or HbA1c test. If uncertain, staff can ask the client for specific information in order mark the appropriate boxes under “age”, “gender”, and “race/ethnicity” (otherwise, staff can complete that information based on their assessment of the client.

For food pantry clients who self-report a history of diabetes, screening will consist of a POC HbA1c test using a finger stick capillary whole blood sample performed by trained personnel.

All clients who participate in screening will receive written results of their screening tests (see Client Screening Results Form in **Appendix J**), along with basic information about their results and local community health care resources.

Additionally, any food pantry client who receives an HbA1c test will receive an educational handout (see **Appendix AK**) with information about the category in which their result falls:

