- HbA1c result less than 5.7%: normal HbA1c range
- HbA1c result 5.7% to 6.4%: pre-diabetes range
- HbA1c result 6.5% to 7.4%: diabetes, controlled
- HbA1c result equal to or greater than 7.5%: diabetes, poorly controlled

Food pantry clients who have screening HbA1c test results $\geq 7.5\%$ will then be further assessed by study staff for eligibility and, if appropriate, enrollment into the study.

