3.1.3 Testing Glycosylated Hemoglobin (HbA1c) Levels

We will measure HbA1c levels for food pantry clients who report a diabetes history or who have a screening RBG result ≥ 160 mg/dL non-fasting or ≥ 140 mg/dL fasting. We will use a point-of-care (POC) HbA1C device using a small sample (1 large drop, 5 microliters [μ L]) of capillary whole blood. Instructions for using the PTS Diagnostics HbA1c+NOW[®]™ system can be found in **section 7.3**.

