Appendix K – Screening Results Form [Spanish]

Gracias por haberse verificado los niveles de azúcar en la sangre y de hemoglobina A1c (A1C) hoy. Su A1C le dice su promedio del nivel de azúcar durante los últimos tres meses. Si su A1C es alto, es posible que usted tenga diabetes. Para las personas que ya tienen diabetes, un objetivo común es tener un A1C cerca de 7%.

El nivel de azúcar en su sangre es: _____ mg/dL (normal es 70 – 160)

Su A1C es: _____ %

- Esto es normal (A1C 5.6% o menos).
- Esto es un poco alto (A1C 5.7% - 6.4%). Es posible que usted tenga pre-diabetes. Le sugerimos que visite su doctor para averiguar si usted tiene pre-diabetes.
- Esto es alto (A1C 6.5% o más alto). Usted puede tener diabetes. Le sugerimos que visite su doctor para averiguar si usted tiene diabetes.

Su A1C resultado de la prueba no es un diagnóstico de pre-diabetes o diabetes. Solo un doctor le puede decir si tiene pre-diabetes o diabetes, o si su diabetes está bien controlada. Por favor consulte la parte atrás de esta forma para información sobre centros comunitarios de salud y más recursos para comida.

(Site Specific Information)

Recursos de Comida

- Banco de alimentos o despensa: Food Bank:
- SNAP (estampillas para comida):
- Programa de Nutrición Suplementar para Mujeres, Bebés, y Niños (WIC):

Centros y Programas de Salud en la Comunidad

- Clinic 1
- Clinic 2
- Clinic 3
- Clinic 4
- Local DPP
- Local DSME Program

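### Minor: the take-home screening form prints one normal glucose range, 70 to 160 mg/dL, with no fasting field, so fasting values of 140 to 160 that the protocol calls elevated appear as normal

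*Combined protocol and SAP*

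**What the plan says.** Section 3.1.1 gives clients with no known diabetes a finger-stick glucose test first. An elevated result is "defined as ≥ 160 mg/dL in non-fasting individuals and ≥ 140 mg/dL in fasting individuals", and it leads to a point-of-care HbA1c test. Section 3.1.3 repeats the rule ("≥ 160 mg/dL non-fasting or ≥ 140 mg/dL fasting"). The footnotes to the Screening Log (Appendix B) and the handout matrix in Appendix AK use the same two limits. The Screening Log and the Screening and Referral Form (Appendix AI) both have a place to mark whether the glucose was taken fasting.

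Section 3.1.1 also says: "All clients who participate in screening will receive written results of their screening tests". The form for this is Appendix J in English and Appendix K in Spanish. Its glucose line has a blank for the value and one reference range, "normal is 70 – 160" in English and "normal es 70 – 160" in Spanish. Neither version has a fasting field. Below it are three HbA1c options, the first of which begins "This is normal (A1C 5.6% or less". The other two cover 5.7% and above and suggest seeing a doctor.

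**The concern.** The form's upper limit is, apart from the boundary value, the protocol's non-fasting limit, applied to everyone. A fasting client between 140 and 160 mg/dL has a result that the protocol treats as elevated, printed beside a range that calls it normal.

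The client most exposed is one whose follow-up HbA1c is below 5.7%. An HbA1c of 5.7% or more is flagged on the same form with a suggestion to see a doctor. Below 5.7% there is no such flag, and the misprinted glucose line is the only place on the form where the elevated finding could show. Appendix AK has a row for exactly this combination of elevated glucose and HbA1c below 5.7%, so the plan expects such clients. At stake is the accuracy of a written health result given to a member of the public. It is not a trial estimate.

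**Working it through.** No sample-size, power or alpha figure is involved. The check sets the form's range against the protocol's limits.

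| Place | Fasting | Non-fasting | Fasting status marked? |
|---|---|---|---|
| Sections 3.1.1 and 3.1.3 | elevated at 140 or more | elevated at 160 or more | limits depend on it |
| Screening Log, Appendix B | HbA1c test at 140 or more | HbA1c test at 160 or more | yes |
| Handout matrix, Appendix AK | elevated at 140 or more | elevated at 160 or more | limits depend on it |
| Results Form, Appendices J and K | normal 70 to 160 | normal 70 to 160 | no |

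**Overlap, in whole mg/dL, reading the printed range as inclusive.**
- Gap between the form's upper limit and the protocol's fasting limit: 160 − 140 = 20 mg/dL.
- Fasting values normal on the form and elevated in the protocol: 160 − 140 + 1 = 21 (140 to 160).
- Non-fasting values in conflict: 160 − 160 + 1 = 1 (only 160).
- If 160 is read as outside the printed range: 159 − 140 + 1 = 20 fasting values and 0 non-fasting values.

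**What the form shows a client with no reported diabetes, fasting, at 140 to 160 mg/dL.**
1. The protocol and the Screening Log call for an HbA1c test. That trigger does not depend on the form, so the test still happens.
2. If HbA1c is 5.7% or more, the glucose line is still wrong, but the HbA1c line flags a high result and suggests a doctor.
3. If HbA1c is below 5.7%, the first HbA1c option applies. To one decimal place, 5.6% or less on the form is the same as section 3.1.1's normal category of less than 5.7%, so that line is right. Only the glucose line is wrong, and nothing on the form flags the elevated value.

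**Effect on the trial.** Under section 3.1.1 only clients with HbA1c of 7.5% or more "will then be further assessed by study staff for eligibility and, if appropriate, enrollment into the study". A client in case 3 is not eligible on that screen.

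**The case against.** The strongest reply is that this has no bearing on the trial. The limits staff act on agree wherever they are stated, and the client left unflagged is not a participant. That stands, and it is why the point is minor.

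The second reply is that the form is never the only message. Sections 3.1.1 and 5.1 have staff tell all screened clients that results are not diagnostic and direct them to a provider. Section 7.2.1 has staff explain the result. Section 3.2.1 gives non-enrolled clients a resource handout and has a referral form faxed for those without a primary care provider. That section sets no HbA1c threshold, although the draft clinic agreement in Appendix O defines at-risk clients by HbA1c of 5.7% or more. Appendix AK adds a MyPlate handout that clients with normal glucose do not get. The form itself says "Only a doctor can tell you whether you have pre-diabetes or diabetes" and lists clinics on its back. All of this stands as mitigation. None of it changes the printed range or tells the client in writing that this glucose value was elevated.

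The third reply is that the meter test is described throughout as a random glucose test, so the form merely leaves out the fasting variant. That is a fair account of how the error probably arose. But the protocol sets a separate fasting limit and the log records fasting status, so the omission still mislabels fasting values.

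A reader might go further and infer that both lines of the form are wrong. They are not: the HbA1c line agrees with section 3.1.1. A reader might also infer that staff end up contradicting the form aloud. The documents contain no script for explaining glucose results, so that would be conjecture.

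**Conclusion.** The point holds as a minor error in a client-facing document. The glucose line of Appendices J and K is wrong for fasting clients at 140 to 160 mg/dL and for non-fasting clients at exactly 160. When HbA1c is below 5.7%, the form gives no sign that the glucose was elevated.

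The 21 and 1 values measure the conflict in the text, assuming whole mg/dL readings and an inclusive printed range. They do not measure how many people are affected: the documents give neither the share of clients screened fasting nor a count of clients in this band.

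Two stronger readings are not supported. One is that HbA1c tests are missed or that enrollment is distorted: the test is triggered by the protocol and log limits, and eligibility rests on HbA1c of 7.5% or more, so testing, eligibility, the primary outcome and the analysis are untouched. The other is that affected clients leave with no pointer to care: the plan has staff direct every screened client to a provider.

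**What to change.** In Appendices J and K:
- Add a fasting / non-fasting tick box beside the glucose value, with fasting as the Screening Log already defines it (more than 8 hours since last intake).
- Replace the single upper limit of 160 with the protocol's own limits: elevated if 140 or more fasting, or 160 or more non-fasting.
- Leave the lower figure of 70 as it is. It is not in dispute and matches the hypoglycemia limit in section 10.1.
- Leave any further advice on the glucose line to the clinical lead.

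The cost is reprinting one form in two languages, with IRB notification if required. Staff already record fasting status on the Screening Log, so no new information has to be collected.
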